## 8.5 Study Population with inclusion and exclusion criteria

### Population-level descriptive epidemiology

All patients with an incident diagnosis of ILD in the period 1st of January 2010 to 31st of December 2022 (or latest date available). Notably, all patients need to have at least 365 days of data visibility (except for CDWBordeaux) prior to the date of their first diagnosis and no prior diagnosis of ILD. This requirement of at least 1 year of prior data history will not hold for children <1 year of age.

	D2.2.3 - Study Protocol for P3-C1-005	
	Author(s): [name] [name]	Version: V2.1
	Dissemination level: Public	

### Patient-level characterisation

The study cohort will include all individuals registered in the database between 1st of January 2010 and 31st of December 2022, with at least 365 days of data visibility (except for CDWBordeaux) and a new ILD diagnosis.

The concept definition of ILD and ILD-subtypes is described in Table S1, [Appendix I](#). The operational definitions of the inclusion and exclusion criteria are presented by means of [Table 5](#) and [Table 6](#), respectively.

**Table 5. Operational Definitions of Inclusion Criteria.**

Criterion	Details	Order of application	Assessment window	Care Settings 	Code Type	Diagnosis position 	Applied to study populations:
Observation period in the database during the period 2010-2022 (or the latest date available)	All individuals present in the period 2010-2022 (or the latest date available)	After	n/a	IP, OP, OT	n/a	n/a	All individuals within selected databases
Prior database history	Study participants will be required to have 365 days of prior history observed before contributing observation time	Prior	[-365, -1]	OP	n/a	n/a	All individuals within CPRD GOLD, BIFAP and IQVIA DA Germany
Washout period	Individuals newly diagnosed with ILD will be required not to have a diagnosis of ILD any time prior to the diagnosis of ILD	Prior	[-inf, -1]	OP	n/a	n/a	All individuals diagnosed with ILD

 IP = inpatient, OP = outpatient, ED = emergency department, OT = other, n/a = not applicable

 Specify whether a diagnosis code is required to be in the primary position (main reason for encounter)

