## 8.4 Follow-up

**Table 4.** Operational Definition of Time 0 (index date) and other primary time anchors.

[figure not shown]
Study population name(s)	Time Anchor Description (e.g. time 0)	Number of entries	Type of entry	Washout window	Care Setting 	Code Type 	Incident with respect to...
All individuals from the respective databases with at least 1 year of valid database history (not for CDWBordeaux).	Study entry date	Single entry	Incident	Anytime prior to study entry date	IP, OP, OT	SNOMED	Diagnosis of ILD
Patients newly diagnosed with ILD	Date of incident ILD	Single entry	Incident	Anytime prior to ILD	IP, OP, OT	SNOMED	Diagnosis of ILD

 IP = inpatient, OP = outpatient, ED = emergency department, OT = other, n/a = not applicable

	D2.2.3 - Study Protocol for P3-C1-005	
	Author(s): [name] [name]	Version: V2.1
	Dissemination level: Public	

To calculate incidence rates, it is important to have an appropriate denominator population and their contributed observation time. Study participants in the denominator population will begin contributing person time on the respective date of the latest of the following: 1) study start date (1st January 2010), 2) date at which they have 1 year of prior history. Participants will stop contributing person time at the earliest date of the following: 1) end of available data in each of the data sources (date of last data extraction), 2) death, 3) study end date (31st December 2022) or 4) date at which the observation period of the specific person ends (individual leaving practice or being diagnosed with ILD whatever comes first)

An example of entry and exit into the denominator population is shown in **Figure 1**. In this example, person ID 1 has already sufficient prior history before the study start date and observation period ends after the study end date, so will contribute during the complete study period. Person ID 2 and 4 enter the study only when they have sufficient prior history. Person ID 3 leaves when exiting the database (the end of observation period). Lastly, person ID 5 has two observation periods in the database. The first period contributes time from study start until end of observation period, the second starts contributing time again once sufficient prior history is reached and exits at study end date.

**Figure 1.** Included observation time for the denominator population.

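### Table 5 limits the ILD washout to outpatient records, against Table 4 and Section 8.5, and the under-1 history waiver covers cases but not person-time

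*Protocol*

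**What the plan says.** **Washout.** Table 5 states the rule as "Individuals newly diagnosed with ILD will be required not to have a diagnosis of ILD any time prior to the diagnosis of ILD", with window [-inf, -1], applied to all individuals diagnosed with ILD. The care-setting cell of that row is OP alone. The table's footnote makes clear that this excludes inpatient and other records: "IP = inpatient, OP = outpatient, ED = emergency department, OT = other, n/a = not applicable". Table 4 (Section 8.4) gives the newly diagnosed cohort the washout "Anytime prior to ILD", with care setting IP, OP, OT. Section 8.5 asks for 365 days of visible data "prior to the date of their first diagnosis and no prior diagnosis of ILD" and names no care setting. Table 1 also requires no earlier ILD diagnosis, again without a setting.

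**Infants.** Section 8.5, under population-level descriptive epidemiology, says: "This requirement of at least 1 year of prior data history will not hold for children <1 year of age". Table 5 says: "Study participants will be required to have 365 days of prior history observed before contributing observation time", for everyone in CPRD GOLD, BIFAP and IQVIA DA Germany. Section 8.4 starts person-time at the later of 1 January 2010 and "2) date at which they have 1 year of prior history". Section 8.1, Table 1 and the denominator row of Table 4 also ask for one year. The only exception any of these gives is CDWBordeaux, which Section 8.8.3 leaves out of the incidence objective.

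**The concern.** The washout is what makes a case incident. If inpatient records do not count towards it, a patient first diagnosed in hospital some years ago can be taken as new. The index date is then late, the characteristics describe an established case, and survival is measured from a point the patient had to survive to reach. CDWBordeaux is the source most open to this. It holds inpatient and outpatient visits, contributes to objectives 2 and 3, and is exempt from the 365-day history rule, so the washout is its only guard against prevalent cases.

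For infants, the numerator and denominator of a rate must come from the same people. A waiver stated for cases but absent from every person-time rule leaves open who is counted. The affected stratum, under 18, is prespecified, and Table S1.A includes ILD codes specific to the perinatal period and infancy.

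**Working it through.** There is no sample size or stated rate to reproduce. The check sets the rules side by side and then bounds the infant effect.

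**Part 1: who is exposed by an OP-only washout in CDWBordeaux**

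Inputs: data collection from 2005 (Section 8.2); study period 1 January 2010 to 31 December 2022 (Section 8.3); cases from IP, OP and OT, single entry (Table 4); follow-up for objectives 2 and 3 from first diagnosis (Table 1); no 365-day rule (Section 8.5).

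| ILD records before 2010 | Record in 2010–2022 | Table 4 / 8.5 | Table 5, literal |
|---|---|---|---|
| None | First is inpatient | New, correct date | New, correct date |
| At least one outpatient | Any | Excluded | Excluded |
| Inpatient only | Any | Excluded | **New, late date** |

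Only the last row differs. These patients carry a record from 2005–2009 and re-enter at their next record from 2010 on, so they should cluster in the early index years. Objective 3 stratifies by calendar time. The protocol gives no count. It does not fix the direction of the survival bias either, because such patients are survivors to re-entry but may also have more advanced disease.

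In the three primary care databases, Section 11 says hospitalisation diagnoses will not be linked. Few inpatient records should therefore be available for the washout to miss.

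**Part 2: infants**

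A child under 1 cannot have 365 days of history. Under Section 8.4 and Table 5, person-time below age 1 is therefore zero, while Section 8.5 admits cases below age 1.

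Let *s* be the infant share of under-18 person-time. If infant cases are counted without person-time, the rate relative to one with infants in both parts is 1/(1 − *s*). The protocol does not give *s*, so these values are assumptions:

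- *s* = 3%: 1/0.97 = 1.031
- *s* = 1/18 = 5.6% (ages evenly spread): 18/17 = 1.059
- *s* = 8%: 1/0.92 = 1.087

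The under-18 rate would be about 3% to 9% too high.

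For all ages, if infants supply 0.8% to 1.2% of person-time (an assumption), the factor is 1/0.992 = 1.008 to 1/0.988 = 1.012, or about 1%.

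The alternative outcome is that infant cases are dropped because they never enter the denominator. The under-18 rate then describes ages 1 to 17 and the waiver has no effect.

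The codes concerned do occur in the incidence databases. Table S2 lists 100 persons for perinatal interstitial emphysema in BIFAP and in IQVIA DA Germany, 100 for interstitial pulmonary fibrosis of prematurity in CPRD GOLD, and 100 for neuroendocrine cell hyperplasia of infancy in BIFAP. The Table 3 footnote says the feasibility counts are rounded up to the nearest hundred, so the true numbers may be much smaller.

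**The case against.** On the washout, one cell stands against Table 1, Section 8.5, Table 4 and the wording of Table 5's own criterion. The same OP entry appears in Table 5's prior-history row, where the criterion is observation time and not a coded visit. That suggests a loosely filled column, and it stands as a likely explanation. It does not settle the matter, because Section 8.5 names Table 5 as the place where the inclusion criteria are made operational.

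A reader might infer that every CDWBordeaux patient whose first ILD code was inpatient gets a wrong index date. The documents do not support that. Table 4 takes inpatient records as cases, so a first inpatient code from 2010 on enters on its correct date. The exposed group is limited to patients with earlier records that were never outpatient.

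On infants, Section 8.8.5 describes cases arising among people who have entered the denominator, and the waiver in Section 8.5 can be read as an exception covering person-time too. Both are fair. They mean that inflation of the under-18 rate is one possible result and cannot be asserted as the expected one. They do not remove the conflict. If infants must enter the denominator first, Sections 8.1 and 8.4 and Table 5 keep them out and the waiver is empty. If the waiver covers person-time, those places state the rule wrongly. On this point Table 4's denominator row agrees with Table 5; the conflict is with Section 8.5.

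**Conclusion.** Both contradictions are in the text and nothing in the protocol resolves them.

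The washout conflict, read literally, lets in CDWBordeaux patients whose only ILD records before 2010 were inpatient. It affects characterisation and survival there, mainly in the early calendar years. Its size cannot be given from the protocol. The effect in the primary care databases is probably small, on the assumption that the absence of hospital linkage leaves few inpatient records in them.

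The infant conflict has two possible outcomes: an under-18 rate about 3% to 9% too high against a rate with infants in both parts, if infants are 3% to 8% of under-18 person-time; or a rate that leaves out cases Section 8.5 says to include. A reader might infer that overall ILD incidence is materially distorted. It is not: the all-ages rate moves by about 1% under the stated assumption.

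The point is worth correcting because all data partners run one released package, and the code needs a single rule.

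**What to change.** 1. In Table 5, change the care setting of the washout row to IP, OP, OT, to match Table 4 and the unrestricted rule in Section 8.5 and Table 1.
2. Apply the under-1 waiver to both cases and person-time, with person-time for these children beginning at start of observation, or to neither. State the choice identically in Sections 8.1, 8.4 and 8.5 and in Tables 1, 4 and 5.

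The cost is a handful of text and table edits and at most one denominator setting in the incidence code. Some CDWBordeaux patients may be reclassified as prevalent and leave the cohort.

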## 8.6 Variables

### 8.6.1 Exposure/s (where relevant)

There is no exposure in this study.

### 8.6.2 Outcome/s (where relevant)

The operational definition of the outcomes is presented in the [Table 6](#).

	D2.2.3 - Study Protocol for P3-C1-005	
	Author(s): [name] [name]	Version: V2.1
	Dissemination level: Public	

**Table 6.** Operational Definitions of Outcome.

Outcome name	Details	Primary outcome?	Type of outcome	Washout window	Care Settings 	Code Type	Diagnosis Position 	Applied to study populations
Death	Death events which occur prior to the end of the study period or the end of individual patient follow-up.	Yes	Time-to-event	No	Primary and secondary	N/A	N/A	Patients with an ILD diagnosis

 IP = inpatient, OP = outpatient, ED = emergency department, OT = other, n/a = not applicable

 Specify whether a diagnosis code is required to be in the primary position (main reason for encounter)

### 8.6.3 Other covariates, including confounders, effect modifiers and other variables

The study covariates are described conceptually, and the context or rationale for the choices are provided in this section. The operational definition of the covariates is described in the [Table 7](#).

#### Covariates for the population-level descriptive epidemiology study (incidence and prevalence)

To characterize ILD and the most common ILD-subtypes (i) alveolitis/pneumonitis excluding aspiration and infectious pneumonitis ii) lung fibrosis and iii) drug induced ILD, the covariates for stratification in population-level descriptive epidemiology study will include age category (<18, 18-39, 40-59, 60-79 and >=80 years at index date), sex and calendar time (year) at start of follow-up.

#### Covariates for the patient-level characterisation study

As part of patient-level characterisation study, comorbidities will be measured in the period of 365 days prior to the index date (i.e. date of diagnosis of ILD). Concomitant medications will be measured within 30 and 365 days prior to the index date and reported for both time periods.

Covariates used to describe Patient characterisation consist of the following:

- Sex
- Age at index date (i.e. date of diagnosis of ILD). Age will be presented in age categories namely:
  - <18
  - 18-39
  - 40-59
  - 60-79
  - >=80 years.
- ILD subtypes:
  - alveolitis/pneumonitis (excluding aspiration and infectious pneumonitis)
  - lung fibrosis
  - drug-induced

	D2.2.3 - Study Protocol for P3-C1-005	
	Author(s): [name] [name]	Version: V2.1
	Dissemination level: Public	

- Unspecified ILD
- description of the top 10 of the most frequent comorbidities and concomitant medications using large-scale characterisation, as specified in the CohortCharacteristics R package and assessed in the period of 365 days prior to the index date.
- Comorbidities of interest (Gaillet, Favelle et al. 2015, Choi, Dauti et al. 2018, Joy, Arbiv et al. 2023), in particular:
  - COPD/emphysema
  - Connective tissue disease namely rheumatoid arthritis, sclerodermia, systemic lupus erythematosus (SLE), polymyositis/dermatomyositis, granulomatosis with polyangiitis (GPA)
  - GERD
  - Hepatitis B/C
  - Cancer excluding non-melanoma skin cancer
- Use of concomitant medication (assessed in the 30 days and 365 days prior to the index date) in particular:
  - chemotherapy
  - amiodarone
  - immune checkpoint inhibitors (ICIs)
  - tyrosine kinase inhibitors (TKIs including crizotinib, EGFR inhibitors, erlotinib, gefitinib)
  - mammalian target rapamycin (mTOR) inhibitors
  - rituximab
  - statins
  - methotrexate
  - nitrofurantoin
  - tumor necrosis factor (TNF)- $\alpha$  antagonists (Paolo, Philippe et al. 2022).

The operational definition of the covariates is described in [Table 7](#). Index date is the start of the incident ILD diagnosis during the study period. The preliminary concepts for prespecified conditions and drugs of interest are described in [Appendix I](#).

	D2.2.3 - Study Protocol for P3-C1-005	
	Author(s): [name] [name]	Version: V2.1
	Dissemination level: Public	

**Table 7.** Operational Definitions of Covariates.

Characteristic	Details	Type of variable	Assessment window	Care Settings 	Code Type	Diagnosis Position 	Applied to study populations
Age category	Assessed at start of follow-up or at date of diagnosis of ILD and categorised to either <18, 18-39, 40-59, 60-79 and >=80 years	Categorical	0	n/a	n/a	n/a	Applied to the general cohort and the cohort of individuals with newly diagnosed ILD.
Sex		Categorical	0	n/a	n/a	n/a	Applied to the general cohort and the cohort of individuals with newly diagnosed ILD
Large scale characterisation	Large-scale patient characterisation with regard to underlying comorbidity and use of concomitant medication	Binary	[-365, 0]	IP, OP, OT	SNOMED	n/a	Individuals with a new diagnosis of ILD
Comorbidity	Specified comorbidities	Binary	[-365, 0]	IP, OP, OT	SNOMED	n/a	Individuals with a new diagnosis of ILD
Concomitant medications	Specified concomitant medication	Binary	[-30, 0], [-365, 0]	IP, OP, OT	RxNorm	n/a	Individuals with a new diagnosis of ILD

IP = inpatient, OP = outpatient, ED = emergency department, OT = other, n/a = not applicable

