## 6. RATIONALE AND BACKGROUND

Interstitial lung disease (ILD) describes a heterogeneous group of respiratory disorders affecting the interstitium of the lungs. (Kaul, Cottin et al. 2021) ILD encompasses many different pathological processes including drug-induced ILDs. (Spagnolo, Bonniaud et al. 2022) Drug-induced interstitial lung disease (DI-ILD) is also a large and very heterogeneous group of adverse drug reactions, ranging from mild to progressive and life-threatening disease. The number of drugs associated with the development of ILD continues to rise, mainly due to the use of novel monoclonal antibodies and biologics for neoplastic and rheumatologic diseases, many of which are associated with lung toxicity, and includes, among others, chemotherapeutics, molecular targeting agents, immune checkpoint inhibitors, antibiotics, antiarrhythmics, and conventional or biologic disease-modifying antirheumatic drugs. (Paolo, Philippe et al. 2022)

There is a geographical variation in the reporting of ILD as an adverse drug reaction in spontaneous case reports, with cases from Japan being more frequently reported. (Pinheiro, Blake et al. 2016, Kaul, Cottin et al. 2021) The assessment of spontaneous case reports requires knowledge of patient characteristics that commonly co-occur with either the disease or the suspected reaction in order to make an informed assessment as to whether such occurrences are drug induced or may simply be due to confounding factors.

A better understanding of the population diagnosed with ILD in Europe and its incidence (including characterising comorbidities, risk factors, medications administered around diagnosis date) may guide signal detection validation discussions for drug-induced ILD within the regulatory network. The EMA has already performed in-house study measuring the incidence of ILD in the IMRD UK, IQVIA France and IQVIA Germany databases (EUPAS50623). (De Jong 2023) This study also included ILD-subtypes allocated by aligned code groups (e.g. codes representing pneumonitis, codes representing pulmonary fibrosis) that may vary in either incidence or recording, and which could also be relevant for patient characterisation. In performing disease epidemiology and patient characterisation study of ILD and ILD-subtypes in Europe, signal detection and validation for potential drug-induced ILD will be better guided.

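### The prespecified chronic comorbidities are searched only in the 365 days up to the ILD diagnosis, so their reported prevalence can only equal or fall below ever-recorded prevalence

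*Protocol*

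**What the plan says.** Section 8.6.3 (Covariates for the patient-level characterisation study) says that "comorbidities will be measured in the period of 365 days prior to the index date". The prespecified list is COPD/emphysema, five named connective tissue diseases, GERD, hepatitis B/C, and "Cancer excluding non-melanoma skin cancer".

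Table 7 repeats the window in operational form. The row "Specified comorbidities" is a binary variable over [-365, 0], so it adds only the index day to the text. The large-scale characterisation has the same window and is "assessed in the period of 365 days prior to the index date", so it offers no longer look-back. Concomitant medications have two windows, [-30, 0] and [-365, 0].

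No section gives any comorbidity a longer window, and section 8.8 contains no sensitivity analysis on look-back. Full history is searched for one purpose: under Table 5, new ILD cases are "required not to have a diagnosis of ILD any time prior to the diagnosis of ILD", with window [-inf, -1].

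Section 11 concedes that some covariates may be underestimated, but it attributes this to the absence of linkage to hospital diagnoses.

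**The concern.** Most of the listed conditions are long-lasting. For such a condition, a one-year search detects whether a code was entered recently, which is not the same as whether the patient has the condition. Someone with rheumatoid arthritis coded six years before ILD, and not coded again in the last year, appears in the table as not having it.

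This bears on the purpose of Objective 2. Section 6 explains that those who assess spontaneous reports need to know which characteristics accompany ILD in order to judge "whether such occurrences are drug induced or may simply be due to confounding factors". Connective tissue disease and cancer are among the competing explanations. If they are under-counted, the reference table is less useful for that judgement. The shortfall also depends on how often each source re-enters a known diagnosis, and the four sources differ in kind: general-practice records, hospital billing codes and outpatient practice records.

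**Working it through.** The protocol gives no prevalence or re-coding figure on this point, so there is no stated figure to reproduce.

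**Direction.** The codes in [-365, 0] are a subset of the codes in [-inf, 0]. Hence prevalence in the 365-day window ≤ ever-recorded prevalence. The inequality is strict as soon as one affected patient has no code in the last year. This needs no assumption.

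**Availability of earlier records.** The 365 days of history is a minimum (Table 1, Table 5), so longer history can exist. Section 8.2 gives data since 1992 for IQVIA DA Germany and from 2005 for CDWBordeaux. The ILD washout already searches all history.

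**Size (rests on assumptions).** Let f be the share of affected patients first coded in the last year. Let r be the mean number of repeat codes per year in the remaining patients, taken as Poisson. Neither is in the protocol. Then

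captured share = f + (1 − f) × (1 − exp(−r)).

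Results over f = 0.05 to 0.20 and r = 0 to 4:

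| r (repeat codes/year) | f = 0.05 | f = 0.10 | f = 0.20 |
|---|---|---|---|
| 0 | 5.0% | 10.0% | 20.0% |
| 0.5 | 42.4% | 45.4% | 51.5% |
| 1 | 65.1% | 66.9% | 70.6% |
| 2 | 87.1% | 87.8% | 89.2% |
| 4 | 98.3% | 98.4% | 98.5% |

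Example for f = 0.10, r = 1: 0.10 + 0.90 × (1 − 0.368) = 0.669.

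**Illustration.** Assume a true prevalence of 10%. Use the feasibility count of 6,900 for CPRD GOLD (Table 3) only to give scale, so 690 patients are affected. With f = 0.10 the 365-day window reports:

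- r = 0: 1.0% (69 patients)
- r = 0.5: 4.5% (313)
- r = 1: 6.7% (462)
- r = 2: 8.8% (606)
- r = 4: 9.8% (679)

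An all-history window reports 10.0% (690) by definition.

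**Comparison with sampling error.** The 95% half-width at 10% is 1.96 × √(0.10 × 0.90 / N). That is 0.94 percentage points at N = 3,900 and 0.63 at N = 8,800, the range in section 8.7. With f = 0.10 the shortfall is 10 − 8.78 = 1.22 points at r = 2, above sampling error. At r = 4 it is 10 − 9.84 = 0.16 points, below it.

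**The case against.** The strongest reply is that this is a deliberate choice and not an error. The window equals the minimum history required, so apart from children under 1 year every eligible patient in CPRD GOLD, BIFAP and IQVIA DA Germany has the same fully observed look-back. Objective 2 in Table 1 can itself be read as referring to the year before diagnosis. For cancer or hepatitis, a past-year target separates current disease from remote or resolved disease. This stands in part. A past-year target would be coherent, but the protocol does not state it or give a reason for it, and it presents the results simply as comorbidities and risk factors.

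Second, nothing in the protocol says how often these diagnoses are re-entered. CDWBordeaux conditions come from billing codes, and Table 3 labels IQVIA DA Germany as claims (section 8.2 describes it as medical records). Such data may repeat a code at each encounter. This stands: infrequent re-coding is an assumption, and the loss may be small for a condition such as active COPD.

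Third, an any-time window has variable length, which can itself create differences between databases. This also stands, and it is a reason to keep the 365-day column.

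Fourth, the ILD washout serves another purpose, the exclusion of prevalent disease. Table 5 therefore shows that earlier records can be searched. It does not make the comorbidity window inconsistent.

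Fifth, section 11 already warns that recording of conditions varies between databases. It does so without mentioning the look-back.

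**Conclusion.** The point holds as a limitation with certain direction and unknown size. Because of the 365-day window, reported prevalence of the prespecified chronic conditions equals or falls below ever-recorded prevalence, and the protocol neither justifies the window nor lists it among its limitations. Under the stated assumptions the captured share runs from about 5% to 98.5%. The low end needs conditions that are hardly ever re-coded, and at about four repeat codes a year the problem disappears.

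A reader might infer more than this:

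- That prevalence will be badly understated for every listed condition. The protocol contains no re-coding rates, and conditions managed at frequent visits may lose almost nothing.
- That ILD will be made to look drug-induced, or that differences between countries will be artefact. The protocol plans no causal attribution and no pooling. These are possible consequences for interpretation and cannot be shown from the text.
- That the 365-day window should be replaced. The fixed window has its own merit, comparability of look-back, and replacing it would trade one limitation for another.

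This is a cheap improvement to Objective 2. It does not undermine the study.

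**What to change.** In section 8.6.3 and Table 7, add an any-time-prior window [-inf, 0] for the prespecified chronic comorbidities, and report it beside the existing [-365, 0] window. Ending at day 0 matches Table 7 and keeps conditions first coded on the date of ILD diagnosis. Report the distribution of available prior history per database. Leave the large-scale characterisation and the medication windows unchanged. Add one sentence to section 11 naming the look-back as a source of possible under-capture in the 365-day column.

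The cost is one further window in the characterisation run and one further column in the baseline table; medications already have a two-window format. The downside is that look-back length in the new column varies by patient and database, notably in CDWBordeaux, which has no minimum history and where even the 365-day window may be only partly observed. Showing both columns with the history distribution lets readers see this.
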